12.3.2 Attribution Definitions

The relationship, or attribution, of an adverse event to the study therapy regimen or study procedure(s) will initially be determined by the site investigator and recorded on the appropriate AE/SAE CRF. Final determination of attribution for safety reporting will be determined by NIAMS. The relationship of an adverse event to study therapy regimen or procedures will be determined using the descriptors and definitions provided in Table 12.3.2.

Table 12.3.2 Attribution of Adverse Events

Code	Descriptor	Relationship (to primary investigational product and/or other concurrent mandated study therapy or study procedure)
UNRELATED CATEGORY		
1	Not related	The adverse event is clearly not related: there is insufficient evidence to suggest a causal relationship.
RELATED CATEGORIES		
2	Possibly/ Probably	The adverse event has a reasonable possibility to be related; there is evidence to suggest a causal relationship.
3	Definitely related	The adverse event is clearly related.

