Figure 4 panel (a) demonstrates the effect of transplantation of antimicrobial CoNS strain(s) on survival of *S. aureus* on the skin surface of subjects with AD. *S. aureus* survival was measured on the lesional sites in both antecubital fossa of the AD subject before and 24 hours after either treatment with antimicrobial CoNS strain(s) autologously screened from the same subject or vehicle. Panel (b) illustrates *S. aureus* survival on the forearm 24 hours after treatment with autologous strain(s) of CoNS or treatment with vehicle. Relative CFU of *S. aureus* is shown as percent of baseline and different color symbols indicates data from each individual subject. In panel (c) CFUs of CoNS on the skin surface of subjects with AD were simultaneously counted as shown in panel (a). Panel (d) shows CoNS survival on the forearm 24 hours after treatment with autologous strain(s) of CoNS or treatment with vehicle. Relative CFU of CoNS is shown as percent of baseline.

In our pilot study of 5 subjects evaluating an AMT cream (IND#15786), we noted no serious adverse events (SAEs). Two subjects noted mild worsening of AD, which were deemed unrelated to the AMT cream given AMT cream was not applied on the area with worsening AD. One subject noted mild worsening of AD with an increase in pruritus and erythema on both arms. Since AMT was applied to only one arm, it is less likely that

the adverse event (AE) was related to the AMT cream given the bilateral worsening of AD on the upper extremities. Overall, the AMT cream was very well tolerated and had no significant adverse events.

2. Study Hypotheses/Objectives

Our preliminary data strongly suggest that some strains of resident CoNS act to defend the skin surface against colonization by SA. The goal of this proposal is to restore this function of the microbiome on atopic skin by replacing these beneficial bacteria. Our approach will be very safe since we will select the beneficial microbes that are normal residents of healthy skin. These bacteria will be harvested from the subject, expanded and reapplied to the same subject. An FDA IND has been approved and institutional IRB obtained for this approach (IND #15786). After application of the bacteria the survival of SA will be measured. Thus, this autologous microbiome transplant (AMT) is a first step before a generalized “probiotic” therapeutic approach.

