11.5. Study Stopping Rules

The study may be prematurely terminated for the following reasons:

Rules for stopping the entire study will include:

- Any serious adverse event for which there is a reasonable possibility that the study product caused the serious adverse event.
- The development of a serious adverse event for which attribution cannot be assessed as definitely unrelated to the study product in 10% or more of the study population.
- The development of any severe (Grade 3) adverse events in 10% or more of the study population.

If any of these criteria for halting the study are met, the study will not be resumed until the relevant information has been discussed with the FDA and the FDA concurs with resumption of the study.

12. Safety Monitoring and Reporting

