12.5 Reporting of Serious Adverse Events and Adverse Events

Recording and Reporting Obligations for SAEs

The investigator will provide the IRB appropriate information concerning any findings that suggest there has been an SAE related to the study.

The investigator will notify the UCSD Human Research Protections Program of any unexpected, fatal or life-threatening experiences in writing no later than 10 working days of the event, according to standard IRB procedures. All serious and medically significant adverse events considered related to the product by the investigator will be followed until resolved or considered stable.

All SAE's will undergo expedited reporting to the NIAMs and the Independent Safety Officer through KAI within 48 hours of the investigator becoming aware of the event.

SAEs that are unanticipated, serious, and possibly related to the study intervention will be reported to the IRB, FDA, and Independent Safety Officer in accordance with requirements. For the IND/IDE:

- 7-day IND Safety Report (unexpected fatal or life-threatening AEs related to the intervention); a copy of the report sent to the FDA will be submitted to the Independent Safety Officer within 24 hours of FDA notification.
- 15-day IND Safety Report (any other serious and unexpected AE related to the intervention); a copy of the report submitted to the FDA will be submitted to the Independent Safety Officer within 24 hours of FDA notification.
- Other AEs documented during the course of the trial will be included in the annual IND report. In the annual AE summary, the Independent Safety Officer Report will state that they have reviewed all AE reports.

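### One attribution code covers both clearly unrelated events and events with insufficient evidence, so an SAE of undetermined cause can be coded Not related and the second halting rule has no code to work from

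*Combined protocol and SAP*

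**What the plan says.** Section 12.3.2 offers three attribution codes. Code 1, the only one in the unrelated category, is defined as "The adverse event is clearly not related: there is insufficient evidence to suggest a causal relationship". Code 2 (possibly or probably related) calls for a reasonable possibility and adds that "there is evidence to suggest a causal relationship". Code 3 is definite. No code exists for unlikely, unknown or unassessable. The site investigator codes first, and "Final determination of attribution for safety reporting will be determined by NIAMS".

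Section 11.5 lists three halting rules, repeated in 12.8.2.2 and 12.8.2.2.1:

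- Rule 1: "Any serious adverse event for which there is a reasonable possibility that the study product caused the serious adverse event". One event is enough.
- Rule 2: an SAE for which "attribution cannot be assessed as definitely unrelated to the study product in 10% or more of the study population".
- Rule 3: Grade 3 events in at least 10% of subjects, with no attribution condition.

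Other actions also depend on relatedness. Section 3.2.1 breaks the blind for unexpected SAEs that the investigator judges related. Section 12.5 describes a "7-day IND Safety Report (unexpected fatal or life-threatening AEs related to the intervention" and a 15-day counterpart with the same relatedness condition. The FDA paragraph of 12.2.1 describes these reports by association with use of the drug, a term the protocol neither defines nor ties to the codes.

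**The concern.** Clear unrelatedness and lack of evidence are different judgements. The first says that the product has been ruled out; the second says that nobody can tell. Rules 1 and 2 assume that these are kept apart: Rule 1 is for plausible causation, and Rule 2 is for a cluster of SAEs in which the product cannot be excluded. The table records the second kind of event under the same code as the first.

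Uncertain cause is foreseeable here. Section 12.2 expects disease flares from withheld medication, and these can be hard to separate from a product effect. The documents do not say how often such an event would be serious. At stake is whether a written halting criterion, in a trial of live bacteria applied twice daily for seven days, can be operated from the trial's own safety data.

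**Working it through.** The plan states no figure to reproduce on this point. The check is a mapping of codes to rules, followed by the 10% thresholds.

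**Step 1: map each kind of SAE to the rules.** Inputs are the codes in 12.3.2, the rules in 11.5 and the grades in 12.3.1. Rule 2 can be read two ways:

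- Reading A: code 1 means definitely unrelated.
- Reading B: Rule 2's own words govern, so an SAE with insufficient evidence is not definitely unrelated.

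| SAE | Meets Rule 1 at first event | Counts to Rule 2, A | Counts to Rule 2, B | Counts to Rule 3, read literally |
|---|---|---|---|---|
| Code 1, clearly unrelated | no | no | no | only if Grade 3 |
| Code 1, insufficient evidence | no | no | yes | only if Grade 3 |
| Code 2 | yes | yes | yes | only if Grade 3 |
| Code 3 | yes | yes | yes | only if Grade 3 |

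Under A, Rules 1 and 2 count the same set, codes 2 and 3. Rule 1 needs one such SAE and Rule 2 needs 10% of subjects, so Rule 1 is always met first. Rule 2 could still be met later, for example after a resumption.

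Under B, Rule 2 can be met without Rule 1. But the first two rows of the table carry the same code, so the recorded data cannot say which code 1 events to count.

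**Step 2: the threshold.** The number of subjects needed is 0.10 × N, rounded up. Sections 3.1, 8.3 and 13.7 give N = 27; sections 4.2 and 13.1 give up to 54.

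- N = 27: 0.10 × 27 = 2.7, so 3 subjects (3/27 = 11.1%; 2/27 = 7.4% is too few).
- N = 54: 0.10 × 54 = 5.4, so 6 subjects (6/54 = 11.1%; 5/54 = 9.3% is too few).

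The protocol also does not say whether the denominator is planned subjects or those enrolled so far.

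**Step 3: what Rule 2 would do if its events could be identified.** The documents give no rate of uncertain SAEs, so the rate p per subject is an assumption, with subjects treated as independent. The chance of reaching the threshold from uncertain SAEs alone is P(X ≥ r), with X binomial (N, p):

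| Assumed p | N = 27, r = 3 | N = 54, r = 6 |
|---|---|---|
| 2% | 0.016 | 0.001 |
| 5% | 0.150 | 0.052 |
| 10% | 0.515 | 0.457 |
| 20% | 0.928 | 0.972 |

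If these events are coded 1 and reading A applies, their contribution to Rules 1 and 2 is zero at every rate. At low rates Rule 2 would seldom be met anyway. At higher rates the choice of denominator also changes the answer.

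**Step 4: the other actions.** If relatedness is taken from the codes, a code 1 SAE is outside the attribution-based unblinding in 3.2.1 and outside the 7- and 15-day reports in 12.5. Under 12.2.1 the result is unclear, because that section's term is not tied to the codes.

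**The case against.** The best reply is that the table does not force the unsafe coding. Code 1 first requires that the event be clearly unrelated, which an unassessable event is not, and the label of code 2 begins with possibly. A cautious investigator could choose code 2, and Rule 1 would then halt the study at the first event. This stands: the defect is that such an SAE can be coded 1, not that it must be. It does not rescue Rule 2, which is then again contained in Rule 1. It also means that the investigator and NIAMS could code the same event differently from the same table.

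The second reply is that several safeguards do not depend on attribution. Rule 3 has no attribution condition. Section 3.2.1 allows emergency unblinding. Section 12.5 sends all SAEs to NIAMS and the Safety Officer within 48 hours, and unexpected, fatal or life-threatening experiences to the institution's research protections office. The Medical Monitor reviews SAE reports (12.8.1), and NIAMS makes the final attribution. All of this stands. These steps ensure that someone sees the event; they do not supply the class that Rule 2 needs. Rule 3 is a partial backstop: it needs 10% of subjects and, read literally, names Grade 3 only, so an SAE of Grade 2, 4 or 5 would not count.

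Third, the sentence in 12.5 that introduces the IND reports speaks of events possibly related. That softens the reporting gap, but possibly is the label of code 2, so a code 1 event is still not plainly covered.

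A reader might also infer from the pilot account in 1.4 ("Since AMT was applied to only one arm, it is less likely that" the event was due to the cream) that the pilot used an intermediate attribution class that has been lost here. The text does not support that. It is narrative about one mild worsening, the pilot reported no SAEs, and no pilot coding scale is shown.

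**Conclusion.** The defect is real and bounded. Code 1 contradicts itself, and an SAE of undetermined cause can be recorded as not related. Such an SAE can miss Rule 1, the attribution-based unblinding, and the 7- and 15-day reports as worded in 12.5. Rule 2 is either redundant as a first trigger (one event for Rule 1 against 3 of 27 or 6 of 54 for Rule 2) or cannot be applied from the recorded codes. This rests on relatedness in 11.5, 3.2.1 and 12.5 being read from the codes in 12.3.2, the only scale the protocol supplies.

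Two stronger conclusions are tempting. One is that uncertain SAEs escape every halting and unblinding trigger; Rule 3 and emergency unblinding show otherwise. The other is that Rule 2 can never fire; it can be met after Rule 1 under reading A and without Rule 1 under reading B. Nor do the documents show that uncertain SAEs would go unseen. The point merits correction because a stated safety rule does not work with the trial's own scale, and the repair is small.

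**What to change.** Separate the two meanings now held in code 1. Clearly not related should be one code, and insufficient evidence or cannot be assessed another, both on the AE/SAE case report form, so that the class Rule 2 already names can be identified from the data.

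Then reconcile the sections that rely on attribution:

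- 12.3.2 with the rules in 11.5, 12.8.2.2 and 12.8.2.2.1;
- 12.3.2 with the relatedness wording in 3.2.1, 12.2.1 and 12.5, so that each term maps to stated codes;
- the 10% denominator, which is 27 or 54 and is not defined as planned or enrolled.

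The content of the halting rules, and when they take effect, is for the sponsor to decide.

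The cost is one table row, one more option on the form and a few sentences. A few more events may count toward ad hoc review. No new data collection or sample size change is needed.

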12.5 Reporting of Serious Adverse Events and Adverse Events

Recording and Reporting Obligations for SAEs

The investigator will provide the IRB appropriate information concerning any findings that suggest there has been an SAE related to the study.

The investigator will notify the UCSD Human Research Protections Program of any unexpected, fatal or life-threatening experiences in writing no later than 10 working days of the event, according to standard IRB procedures. All serious and medically significant adverse events considered related to the product by the investigator will be followed until resolved or considered stable.

All SAE's will undergo expedited reporting to the NIAMs and the Independent Safety Officer through KAI within 48 hours of the investigator becoming aware of the event.

SAEs that are unanticipated, serious, and possibly related to the study intervention will be reported to the IRB, FDA, and Independent Safety Officer in accordance with requirements. For the IND/IDE:

- 7-day IND Safety Report (unexpected fatal or life-threatening AEs related to the intervention); a copy of the report sent to the FDA will be submitted to the Independent Safety Officer within 24 hours of FDA notification.
- 15-day IND Safety Report (any other serious and unexpected AE related to the intervention); a copy of the report submitted to the FDA will be submitted to the Independent Safety Officer within 24 hours of FDA notification.
- Other AEs documented during the course of the trial will be included in the annual IND report. In the annual AE summary, the Independent Safety Officer Report will state that they have reviewed all AE reports.

12.6 Pregnancy Reporting

The investigator shall be informed immediately of any pregnancy in all study subjects or a partner of a study subject. A pregnant subject shall be instructed to stop taking study medication. The investigator shall counsel the subject and discuss the risks of continuing with the pregnancy and the possible effects on the fetus. Monitoring of the pregnant subject shall continue until the conclusion of the pregnancy.

The investigator will report to NIAMS within 1 business day of notification of the event.

12.8 Review of Safety Information

12.8.1 Medical Monitor Review

The Safety Officer shall receive bi-annual reports from the investigator compiling new and accumulating information on AEs, SAEs, and pregnancies recorded by the study site.

In addition, the Medical Monitor ([name] M.D.) shall review and make decisions on the disposition of the SAE and pregnancy reports.

12.8.2 Safety Officer Review

12.8.2.1 Planned Safety Officer Reviews

The Safety Officer shall review safety data at least yearly during planned Safety Officer (SO) Data Review Meetings. Data for the planned safety reviews will include, at a minimum, a listing of all reported AEs and SAEs.

The SO will be informed of an Expedited Safety Report in a timely manner

12.8.2.2 *Ad hoc* Safety Reviews

Triggers for ad hoc review:

- Any serious adverse event for which there is a reasonable possibility that the study product caused the serious adverse event.
- The development of a serious adverse event for which attribution cannot be assessed as definitely unrelated to the study product in 10% or more of the study population.
- The development of any severe (Grade 3) adverse events in 10% or more of the study population.

If any of these criteria for halting the study are met, the study will not be resumed until the relevant information has been discussed with the IRB, Safety Officer, NIAMS, and the FDA and these bodies concur with resumption of the study.

After review of the data, the Safety Officer will make recommendations regarding study conduct and/or continuation.

12.8.2.2.1 Temporary Suspension of enrollment and drug dosing for ad hoc Safety Review

The following are events that could trigger a safety review, resulting in temporary suspension of enrollment and drug dosing

- Any serious adverse event for which there is a reasonable possibility that the study product caused the serious adverse event.
- The development of a serious adverse event for which attribution cannot be assessed as definitely unrelated to the study product in 10% or more of the study population.
- The development of any severe (Grade 3) adverse events in 10% or more of the study population.

A temporary halt *in enrollment and drug dosing* will be implemented if an *ad hoc* SO safety review is required. No new participants will be consented during this time and subjects will be instructed to stop application of the cream until the IRB, FDA, and Safety Officer concur that study procedures may be resumed.

13. Statistical Considerations and Analytical Plan

13.1 Overview

We propose here a randomized, double-blind, placebo-controlled trial that will apply beneficial bacteria from the AD host onto lesional skin of AD patients, thus performing an autologous microbiome transplant. Up to 54 subjects with AD will be recruited.

13.2 Endpoints/Outcomes

13.2.1 Primary Endpoint(s)/Outcome(s)

- The change in *S. aureus* abundance after 7 days of AMT cream by using skin swabs to determine the quantity of *S. aureus* using culture and qPCR.

13.2.2 Secondary Endpoint(s)/Outcome(s)

Secondary Lesional AD skin:

1. The abundance of the AMT bacterial strains on lesional skin at baseline and after 1 week BID application of AMT.
2. The quantity of transplanted bacteria on lesional skin after stopping AMT cream 1 day, 2 days, and 4 days after last application.
3. The change in abundance of *Staph aureus* on lesional skin from baseline to 1 day, 2 days, and 4 days after stopping AMT.
4. Change in clinical assessments, including SCORAD, modified EASI, and EASI after 1 week BID application of AMT.
5. Identify lesional skin microbiome by DNA sequencing from baseline and after 1 week BID application of AMT.
6. Evaluate the lesional skin microbiome transcriptome by RNA-sequencing analysis from baseline and after 1 week BID application of AMT.

Secondary Non-lesional skin:

1. The abundance of *Staph aureus* at baseline and after 1 week BID application of AMT on non-lesional skin.
2. The abundance of AMT bacterial strains on non-lesional skin at baseline and after 1 week BID application of AMT.
3. The quantity of transplanted bacteria on non-lesional skin after stopping AMT cream 1 day, 2 days, and 4 days after last application.
4. The change in abundance of *Staph aureus* on non-lesional skin from baseline to 1 day, 2 days, and 4 days after stopping AMT.
5. Identify non-lesional skin microbiome by DNA sequencing from baseline and after 1 week BID application of AMT.
6. Evaluate the non-lesional skin microbiome transcriptome by RNA-sequencing analysis from baseline and after 1 week BID application of AMT.

13.3 Measures to Minimize Bias

Subjects will be randomized into a 2:1 allocation ratio of AMT cream to placebo. Both subjects and investigators making clinical assessments will be blinded.

13.4 Analysis Plan

13.4.1 Analysis Populations.

Screening Population: The Screening Population will consist of all subjects who sign informed consent. Subject disposition, demographics, and safety measures will be summarized for this

population. Additionally, differences between screened and randomized subjects and between screened and not randomized subjects will be examined.

Safety Population: All randomized subjects who provide any safety data will be included in the Safety Population. A subject will not be required to complete all safety assessments to be included in this population. Analyses of this population will be classified according to the treatment actually received.

Efficacy Population: An intention-to-treat analysis will be conducted that includes all subjects who had at least one follow-up visit after intervention. A per-protocol analysis will also be conducted that includes all subjects who were compliant with the full intervention regimen with no major protocol violations.

13.4.2 Primary Analysis of Primary Endpoint(s)/Outcome(s)

Aim: The change in *S. aureus* abundance after 7 days of AMT cream by using skin swabs to determine the quantity of *S. aureus* using culture and qPCR.

For each AD subject, the abundance of *S. aureus* will be calculated using CFU counts from baseline (day 28) to Day 35 after 7 days of AMT cream application or placebo application. Comparisons of *S. aureus* reduction will be made between AMT cream and placebo subjects using a two-tailed t-test for independent samples with type II error rate of 0.2 and type I error rate of 0.05. The sample size will include 18 subjects in the AMT cream arm and 9 subjects in the placebo arm. Comparisons of AMT cream versus placebo cream will be reported as means, standard deviations, medians, and minimum and maximum. An intention-to-treat analysis will be conducted that includes all subjects who had at least one follow-up visit after intervention. A per-protocol analysis will also be conducted that includes all subjects who were compliant with the full intervention regimen with no major protocol violations.

